#### **4.3.4        Post-Trial Access to Atezolizumab**

The Sponsor will offer *continued access to Roche IMP (atezolizumab) free of charge to eligible patients in accordance with the Roche Global Policy on Continued Access to Investigational Medicinal Product, as outlined below.*

*A patient will be eligible to receive Roche IMP (atezolizumab) after completing the study if all of the following conditions are met:*

- *The patient has a life-threatening or severe medical condition and requires continued Roche IMP treatment for his or her well-being*
- *There are no appropriate alternative treatments available to the patient*
- *The patient and his or her doctor comply with and satisfy any legal or regulatory requirements that apply to them*

*A patient will not be eligible to receive Roche IMP (atezolizumab) after completing the study if any of the following conditions are met:*

- *The Roche IMP is commercially marketed in the patient's country and is reasonably accessible to the patient (e.g., is covered by the patient's insurance or wouldn't otherwise create a financial hardship for the patient)*
- *The Sponsor has discontinued development of the IMP or data suggest that the IMP is not effective for UC*
- *The Sponsor has reasonable safety concerns regarding the IMP as treatment for UC*
- *Provision of the Roche IMP is not permitted under the laws and regulations of the patient's country*

*The Roche Global Policy on Continued Access to Investigational Medicinal Product is available at the following website:*

*[http://www.roche.com/policy\\_continued\\_access\\_to\\_investigational\\_medicines.pdf](http://www.roche.com/policy_continued_access_to_investigational_medicines.pdf)*

*Patients may be eligible to receive atezolizumab as part of an extension study, if no other option in the country is possible.*

## **4.4 CONCOMITANT THERAPY**

Concomitant therapy includes any prescription medications or over-the-counter preparations used by a patient between the 7 days preceding the screening evaluation and the treatment discontinuation visit. All such medications should be reported to the investigator and recorded on the Concomitant Medications eCRF.

### **4.4.1 Permitted Therapy**

Patients who experience infusion-associated symptoms may be treated symptomatically with acetaminophen, ibuprofen, diphenhydramine and/or famotidine or another H2 receptor antagonist, as per standard practice (equivalent medications may be substituted per local practice). Serious infusion-associated events manifested by dyspnea, hypotension, wheezing, bronchospasm, tachycardia, reduced oxygen saturation or respiratory distress should be managed with supportive therapies as clinically indicated (e.g., supplemental oxygen and  $\beta$ 2-adrenergic agonists; see [Appendix 6](#)).

Systemic corticosteroids and tumor necrosis factor- $\alpha$  inhibitors may attenuate potential beneficial immunologic effects of treatment with atezolizumab, but may be administered at the discretion of the treating physician after consultation with the Medical Monitor (see Exclusion Criterion 21 [Section [4.1.2](#)]). If feasible, alternatives to corticosteroids should be considered. Premedication may be administered for cycles  $\geq 2$  at the discretion of the treating physician after consultation with the Medical Monitor. The use of inhaled corticosteroids for COPD and mineralocorticoids (e.g., fludrocortisone) and low-dose corticosteroids for patients with orthostatic hypotension or adrenocortical insufficiency is

allowed. Megestrol administered as an appetite stimulant is acceptable while the patient is enrolled in the study.

Colony-stimulating factors, such as granulocyte colony-stimulating factor and erythropoietin, should only be used according to manufacturers' labels and the ASCO and ASCO/ASH guidelines ([Smith et al. 2006](#); [Rizzo et al. 2010](#)).

*Inactivated vaccinations (such as influenza, COVID-19) are permitted. Live, attenuated vaccines are not permitted (see Section 4.4.2).*

*Patients experiencing a mixed response requiring local therapy for control of three or fewer lesions may still be eligible to continue study treatment at the investigator's discretion. The Medical Monitor is available to advise as needed. Patients who receive local therapy directed at a target lesion will no longer be evaluable for radiographic response but will remain evaluable for progression.*

Patients who use hormonal therapy with gonadotropin-releasing hormone agonists or antagonists for prostate cancer, oral contraceptives, hormone-replacement therapy, prophylactic or therapeutic anticoagulation therapy (such as low molecular weight heparin or warfarin at a stable dose level), or other allowed maintenance therapy (see Section 4.1.2) should continue their use.

All concomitant medications should be reported to the investigator and recorded on the appropriate eCRF.

#### **4.4.2 Prohibited Therapy**

Any concomitant therapy intended for the treatment of cancer, whether health authority-approved or experimental, is prohibited. This includes but is not limited to the following:

- Chemotherapy, hormonal therapy, immunotherapy, radiotherapy, or investigational agents (except for maintenance therapies outlined in Section 4.1.1 and 4.1.2)
  - After completion of Cycle 1, certain forms of radiotherapy may be considered for palliation if patients are deriving benefit (e.g., treatment of known bone metastases or symptomatic hematuria)
- Traditional herbal medicines are not recommended because the ingredients of many herbal medicines are not fully studied, and their use may result in unanticipated drug-drug interactions that may cause or confound assessment of toxicity
- Patients who are receiving a receptor activator of nuclear factor kappa B ligand inhibitor (denosumab) prior to enrollment must be willing and eligible to receive a bisphosphonate instead while on study; denosumab could potentially alter the activity and the safety of atezolizumab
- Patients should not receive abatacept or belatacept treatment (those who were receiving it must stop it > 8 weeks before study entry)

Live, attenuated vaccines (e.g., FluMist®) are prohibited within 4 weeks prior to initiation of study treatment, during atezolizumab treatment, and for 5 months after the discontinuation of atezolizumab.

Patients are not allowed to receive immunostimulatory agents, including but not limited to interferon (IFN)- $\alpha$ , IFN- $\gamma$ , or IL-2, during the entire study. These agents, in combination with atezolizumab, could potentially increase the risk for autoimmune conditions.

With the exception of autoimmune disease patients, patients should not receive immunosuppressive medications, including but not limited to cyclophosphamide, azathioprine, methotrexate, and thalidomide. These agents could potentially alter the activity and the safety of atezolizumab.

Systemic corticosteroids, immunosuppressive medications, and TNF- $\alpha$  inhibitors may attenuate potential beneficial immunologic effects of treatment with atezolizumab. Therefore, in situations in which systemic corticosteroids, immunosuppressive medications, or TNF- $\alpha$  inhibitors would be routinely administered, alternatives, including antihistamines, should be considered. If the alternatives are not feasible, systemic corticosteroids, immunosuppressive medications, and TNF- $\alpha$  inhibitors may be administered at the discretion of the investigator after consultation with the Medical Monitor. If feasible, alternatives to these agents should be considered.

*Systemic corticosteroids or immunosuppressive medications are recommended, at the discretion of the investigator, for the treatment of specific adverse events when associated with atezolizumab therapy.*

Patients with CNS metastases are allowed to receive anticonvulsants and steroid treatments if the dose of prednisone is  $\leq$  20 mg / day (or equivalent).

In addition, all patients (including those who discontinue the study early) should not receive other immunostimulatory agents for 10 weeks after the last dose of atezolizumab.

The above list of medications is not necessarily comprehensive. The investigator should consult the prescribing information for any concomitant medication and contact the Medical Monitor if questions arise regarding medications not listed above.

#### **4.5 STUDY ASSESSMENTS**

Please see [Appendix 1](#) for the schedule of assessments performed during the study.

#### **4.5.1        Informed Consent Forms and Screening Log**

Written informed consent for participation in the study must be obtained before performing any study-related procedures. Informed Consent Forms for enrolled patients and for patients who are not subsequently enrolled will be maintained at the study site.

All screening evaluations must be completed and reviewed to confirm that patients meet all eligibility criteria before enrollment. The investigator will maintain a screening log to record details of all patients screened and to confirm eligibility or record reasons for screening failure, as applicable.

#### **4.5.2        Medical History and Demographic Data**

Medical history includes clinically significant diseases (including autoimmune diseases), surgeries, cancer history (including prior cancer therapies and procedures), reproductive status, smoking history, and all medications (e.g., prescription drugs, over-the-counter drugs, vaccines, herbal or homeopathic remedies, nutritional supplements) used by the patient within 7 days prior to the screening visit. A history of pleural or pericardial effusion or of ascites requiring intervention should be entered in the medical history.

Cancer history will include an assessment of prior treatment with bacillus Clamette-Guerin (BCG).

To further evaluate medical history, Investigators should determine an age-adjusted Charlson comorbidity index for each subject during screening ([Koppie et al. 2008](#)). Refer to [Appendix 9](#) for the AACI worksheet.

Demographic data will include age, ECOG performance status, sex, and self-reported race/ethnicity.

#### **4.5.3        Physical Examinations**

A complete physical examination should be performed at screening and should include an evaluation of the head, eyes, ears, nose, and throat, and the cardiovascular, dermatological, musculoskeletal, respiratory, gastrointestinal, genitourinary, and neurological systems. Any abnormality identified at baseline should be recorded on the General Medical History and Baseline Conditions eCRF. Height and weight should be measured and recorded in the eCRF.

At subsequent visits (or as clinically indicated), limited, symptom-directed physical examinations should be performed. Changes from baseline abnormalities should be recorded in patient notes. New or worsened clinically significant abnormalities should be recorded as adverse events on the Adverse Event eCRF.

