### **IMvigor 210 (Cohort 2)**

The median duration of treatment in IMvigor 210 was 12 weeks (range 0–66 weeks) at the study's cutoff date (14 September 2015). All-cause, any grade AEs were reported in 300 (97%) of 310 patients, with 170 (55%) patients experiencing a grade 3–4 AE. Two-hundred fifteen (69%) patients had a treatment-related AE of any grade, and 50 (16%) had a grade 3–4 treatment-related AE ([Table 3](#)).

**Table 3 Treatment-Related Adverse Events in 310 Patients who Received Atezolizumab in IMvigor 210 (14 September 2015 Data Cut)**

	Any grade n (%)	Grade 3–4 n (%)
Any adverse event	215 (69%)	50 (16%)
Fatigue	93 (30%)	5 (2%)
Nausea	42 (14%)	0
Decreased appetite	36 (12%)	2 (1%)
Pruritis	31 (10%)	1 (<1%)
Pyrexia	28 (9%)	1 (<1%)
Diarrhea	24 (8%)	1 (<1%)
Rash	23 (7%)	1 (<1%)
Arthralgia	21 (7%)	2 (1%)
Vomiting	18 (6%)	1 (<1%)
Dyspnea	10 (3%)	2 (1%)
Anaemia	9 (3%)	3 (1%)
Aspartate aminotransferase increased	10 (3%)	2 (1%)
Pneumonitis	7 (2%)	2 (1%)
Hypotension	5 (2%)	2 (1%)
Hypertension	3 (1%)	3 (1%)
Colitis	3 (1%)	2 (1%)

Adverse events reported up until data cutoff on 14 September 2015

Ninety-three (30%) patients had an AE leading to dose interruption, and 11 (4%) had an AE that led to treatment withdrawal. Treatment-related serious adverse events (SAEs) were reported in 34 (11%) of 310 patients. No cases of febrile neutropenia were reported, and no treatment-related deaths occurred during the study.

Twenty (6%) patients had an immune-mediated AE of any grade, with pneumonitis (n=5 [2%]), dyspnea (n=3 [1%]) and increased aspartate aminotransferase (n=3 [1%]) being the most common. Thirteen (4%) patients had a grade 3–4 immune-mediated AE of any cause, including colitis, autoimmune hepatitis, hepatitis, cytokine release syndrome, pericardial effusion, and paraplegia (n=1 for each). No immune-mediated renal toxicity was observed. Sixty-nine (22%) of 310 patients had an AE that necessitated systemic steroid use.

Please refer to the Atezolizumab Investigator's Brochure for more information on the safety of atezolizumab across the clinical development program, including the occurrence of serious, related and unexpected events.

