### **2.1 PRIMARY OBJECTIVE**

The primary objective of this study is to evaluate the safety of atezolizumab based on the following endpoints:

- Nature, severity, duration, frequency and timing of adverse events (AEs)
- Changes in vital signs, physical findings, and clinical laboratory results during and following atezolizumab administration

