## **6.4 PRIMARY SAFETY ANALYSIS**

The primary endpoint of the study is the incidence of treatment-emergent AEs. Verbatim descriptions of AEs will be mapped to MedDRA thesaurus terms and graded according to the National Cancer Institute Common Terminology Criteria version 4.0. Multiple occurrences of the same event will be counted once at the maximum severity.

Other safety variables will include:

- Drug exposure (e.g., treatment duration, number of doses, dose intensity and dose modifications/discontinuations, with reasons)
- All AEs
- SAEs
- AEs (grade 3–5)
- AEs of special interest
- AEs leading to study drug discontinuation or interruption
- Changes in vital signs from baseline
- Changes in physical findings from baseline
- Changes in selected laboratory parameters from baseline
- Deaths and cause of death
- Concomitant medications

The incidence of AEs will be summarized by frequency tables. Corresponding 95% Clopper-Pearson confidence intervals (CIs) will be presented, as applicable. Time to first incidence of selected event types will also be estimated and presented graphically using the Kaplan-Meier method.

Treatment exposure, discontinuation rate, and cause of death will be analyzed by frequency tables. When appropriate, median time on treatment and 95% CI will be estimated by the Kaplan-Meier approach or using univariate statistics, presenting mean, median, quartiles, minimum, maximum and standard deviation.

Changes in vital signs and physical findings from baseline will be tabulated and presented graphically when applicable.

Worst grades for laboratory parameters and newly occurring Grade 3 and 4 laboratory values during treatment will be summarized by frequency tables.

Concomitant medications recorded during the study will be summarized by frequency tables.

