AEs with onset on first dosing date, not recorded as starting before study treatment administration will be considered as TEAEs. Similarly, AEs with onset date prior first dosing date but worsening/change recorded on or after first dosing date will be considered as TEAEs.

Only TEAEs will be included in summary tables. AEs which are not treatment-emergent will only be included in the AE listings.

Patient rates for AEs will be presented and accompanied by the respective two-sided 95% Pearson-Clopper CIs.

In any AE summary tables, number and percentage of patients reporting at least one AE will be provided. In AE summary tables by SOC and PT, the number of reported events will be presented additionally.

Every occurrence of an AE in any patient will be counted in the total number of events.

In tables presenting frequency of AEs by worst grade, only the event with the highest grade will be counted when there are multiple occurrences of a same AE in one patient.

A missing NCI CTCAE grade will be imputed as follows: for a fatal AE, as Grade 5; for a non-fatal AE, as Grade 4.

A summary table will be provided presenting:

- Number and percentage of patients with any TEAE
- Number and percentage of patients with any Serious TEAE
- Number and percentage of patients with any related TEAE
- Number and percentage of patients with any related Serious TEAE
- Number and percentage of patients with any TEAE leading to study drug discontinuation
- Number and percentage of patients with any grade 3 to 4 TEAE
- Number and percentage of patients with any grade 5 TEAE
- Number and percentage of patients with any AESI
- Number and percentage of patients with any grade 3 to 5 AESI
- Number and percentage of deaths, overall and by reason
- Number and percentage of deaths on study treatment (i.e. within 30 days post last study treatment administration), overall and by reason

Following safety data will be summarized:

- TEAEs by SOC, PT and by worst grade
- TEAEs of grade 3 to 5, by PT and by worst grade
- TEAEs of grade 5, by PT
- TEAEs leading to study drug discontinuation, by SOC and PT
- TEAEs leading to study discontinuation, by SOC and PT
- TEAEs related to study drug, by SOC, PT and worst grade
- Serious TEAEs by SOC, PT and worst grade
- Serious TEAEs related to study drug, by SOC and PT
- AEs of special interest by category, PT and worst grade (with additional column for AESI of grade ≥ 3)

Death cases will be summarized as follows:

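### The SAP plans no output for adverse events leading to study drug interruption, a safety variable that Protocol 6.4 lists; the promised physical-findings tabulation also needs aligning

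*Protocol*

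**What the plan says.** **Interruption.** Protocol 6.4 names incidence of treatment-emergent adverse events as the primary endpoint. Its list of other safety variables then includes "AEs leading to study drug discontinuation or interruption". The matching row of the summary table in SAP 4.6.2 is "Number and percentage of patients with any TEAE leading to study drug discontinuation". The other SAP 4.6.2 outputs by consequence are tables for drug discontinuation and for study discontinuation, and a listing for permanent treatment discontinuation. The summary table is repeated for each subgroup. In the SAP, the wording that includes interruption survives only in the version 9 synopsis reproduced as Appendix 1.

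**Physical findings.** Protocol 2.1 places "Changes in vital signs, physical findings, and clinical laboratory results during and following atezolizumab administration" under the primary objective, and SAP 2.2.5 repeats this. Protocol 6.4 adds: "Changes in vital signs and physical findings from baseline will be tabulated and presented graphically when applicable". Protocol 4.5.3 sets the data route in three sentences, which Appendix 1 footnote f repeats. The rule for the screening examination is "Any abnormality identified at baseline should be recorded on the General Medical History and Baseline Conditions eCRF". For later visits, the general rule is "Changes from baseline abnormalities should be recorded in patient notes". A different destination applies to deterioration that matters clinically: "New or worsened clinically significant abnormalities should be recorded as adverse events on the Adverse Event eCRF".

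**The concern.** The purpose of this trial is to describe safety in a population broader than earlier studies allowed, including ECOG 2, renal impairment and controlled autoimmune disease. Protocol 5.1.2 rules out dose modification but lets treatment be suspended for toxicity, and Appendix 11 specifies withholding for many events. Short of permanent discontinuation, a pause in dosing is therefore the main way toxicity alters treatment here. If the SAP is run as written, the report will show which events ended treatment but not which events paused it, by term, by grade or by subgroup. Protocol 6.4 specified that information.

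The physical-findings item is a lesser mismatch. The protocol promises a change-from-baseline tabulation for which the SAP has no output and the protocol names no complete data source.

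**Working it through.** No printed figure is in dispute. As a check on the plan's precision statement, exact Clopper-Pearson limits reproduce every row of Protocol Table 6. For 5/1000 they give 0.163% to 1.163%, half-width 0.500%, matching the stated ±0.5%.

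**1. Tracing the variable through SAP 4.6.2**

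| Planned output | Discontinuation | Interruption |
|---|---|---|
| Summary table | yes | none |
| Tables by system organ class and preferred term | yes (drug; study) | none |
| By-patient listings by consequence | yes (permanent) | none |
| Subgroup repeats of the summary table | yes | none |

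**2. Whether SAP 4.6.1 supplies a substitute**

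- It counts patients with a modified infusion and patients with a modified dose, by reason. Neither count carries an event term or grade, and neither is said to include a withheld dose. Protocol 5.1.2 treats dose modification and treatment interruption under separate headings, so a count of modifications cannot be assumed to contain interruptions. Protocol 6.4 also lists dose modifications under drug exposure, apart from the adverse event variable.
- A cycle is counted only when a dose is given, so a skipped dose leaves no counted cycle.
- Planned dose is (last dose date − first dose date + 21) × 1200 / 21. Relative dose intensity therefore falls when a dose is delayed, but it does not show why. A hold that is never followed by another dose does not enter the formula at all.

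**3. Likely size**

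The input is Protocol 1.3.4 on IMvigor 210 cohort 2: "Ninety-three (30%) patients had an AE leading to dose interruption, and 11 (4%) had an AE that led to treatment withdrawal", with 310 patients as denominator.

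- Interruption: 93/310 = 30.0% (exact 95% CI 24.95% to 35.44%).
- Withdrawal: 11/310 = 3.5%, printed as 4% (1.78% to 6.26%).
- Ratio: 93/11 = 8.5.
- Overlap between the groups is not reported. If disjoint, patients with either number 93 + 11 = 104, and withdrawals are 11/104 = 10.6% of them. If every withdrawn patient also had an interruption, the share is 11/93 = 11.8%.
- Assuming the same rates in about 1000 patients, an interruption table would cover about 300 patients (300/1000: 27.17% to 32.95%). The discontinuation table would cover about 35 (35/1000: 2.45% to 4.83%). Taking the earlier study's own intervals instead, the ranges are about 250 to 354 and 18 to 63.

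**4. Physical findings, by destination**

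- Baseline abnormality: medical history eCRF.
- New or worsened and clinically significant: Adverse Event eCRF, and so available to the SAP 4.6.2 tables and listings.
- Improvement, or a change that is not clinically significant: patient notes, with no eCRF named.
- Output: SAP 4.6.1 to 4.6.5 contain no physical-findings table or listing. SAP 4.6.4 covers vital signs, height and weight.

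A full change-from-baseline table therefore lacks both an output and part of its source. Clinically significant worsening lacks neither.

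**The case against.** The strongest reply is that little is actually lost. The primary endpoint is untouched. The SAP tabulates serious, related, grade 3 to 5, fatal and special-interest events and lists all adverse events by patient. Exposure output shows modifications by reason and relative dose intensity. Later examinations are limited and symptom-directed, so adverse event reporting is a sensible route for physical findings.

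Most of this stands. It limits the point to a missing output for a listed secondary safety variable. It does not close the gap, because none of those outputs identifies which events, at what grade, led to a hold.

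Three stronger readings are tempting and are not supported.

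- From the patient-notes sentence alone, a reader might infer that changes in physical findings are kept only in notes and that a primary-objective endpoint has no data. The next sentence in Protocol 4.5.3 sends clinically significant deterioration to the Adverse Event eCRF.
- A reader might infer that interruption results cannot be produced. The documents show a missing table, not missing data. Equally, they do not describe an action-taken field on the adverse event form, so its existence should be confirmed and not presumed.
- A reader might turn the ratio into a claim that discontinuation tables show one eighth of treatment-modifying toxicity. A ratio of two counts is not a share. With the overlap unknown, the share in the earlier study lies between 10.6% and 11.8%, and that study had narrower eligibility.

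**Conclusion.** The point holds as a protocol-to-SAP omission. Adverse events leading to interruption are specified in Protocol 6.4 and have no table, listing or subgroup summary in the SAP body, and the exposure counts do not replace one. The omitted part is probably the larger part of the combined variable. That judgement rests on the 93 versus 11 of 310 in IMvigor 210, and on the assumptions that interruption means the same thing in both studies and that the relative frequency carries over to a broader population. The figures of about 300 and 35 patients are for scale only. Sample size, precision and the primary endpoint are unaffected.

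The physical-findings item is secondary. The text needs aligning, but no result that the SAP plans would change. The correction to interruption reporting should be made before the final analysis.

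**What to change.** **Interruption.** First confirm that the adverse event form captures action taken, in a way that separates a temporary hold from permanent discontinuation. Then, in SAP 4.6.2:

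- add a row for patients with any treatment-emergent event leading to study drug interruption to the summary table, which carries it into the subgroup repeats;
- add a table by system organ class and preferred term;
- add a by-patient listing;
- state in SAP 4.6.1 whether a withheld dose counts as a modification.

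If action taken proves not to have been collected, say so in the SAP and record the variable as not reportable. Otherwise the cost is one row, one table, one listing and a sentence.

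**Physical findings.** State in the SAP that they are reported through adverse events, as new or worsened clinically significant abnormalities, and that no separate change-from-baseline table will be produced. Reconcile Protocol 2.1, Protocol 6.4 and SAP 2.2.5 with that statement. The SAP sentence costs little. Changing the protocol wording is an amendment that goes through the approvals in Protocol 9.7, so it could be held for the next amendment, with the difference recorded in the SAP meanwhile. Neither change alters any clinical rule.
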